1.8. Benefit-risk Assessment

Healthy subjects and subjects with suspected NASH and liver fibrosis in the current study will not receive any health benefit (beyond that of an assessment of their medical status) from participating in the study. The risks of participation are primarily those associated with adverse reactions to the investigational medicinal product (IMP), although there may also be some discomfort from collection of blood samples and other study procedures. More

information about the known and expected benefits, risks, and reasonably anticipated adverse effects associated with GB1211 may be found in the IB.⁶

2. OBJECTIVES AND ENDPOINTS

2.1. Objectives

The primary objectives of the study are:

- to evaluate the safety and tolerability of single and multiple doses of GB1211 administered to healthy subjects.
- to evaluate the safety and tolerability of multiple doses of GB1211 administered to subjects with suspected NASH and liver fibrosis.

The secondary objectives of the study are:

- to evaluate the PK of single doses of GB1211 in plasma and urine in healthy subjects and the PK of multiple doses of GB1211 in plasma of healthy subjects and subjects with suspected NASH and liver fibrosis.
- to determine the effect of food on the single oral dose PK of GB1211.

The exploratory objectives of the study are:

- to investigate biomarkers related to GB1211 activity at single and/or multiple doses in comparison to placebo in healthy subjects and subjects with suspected NASH and liver fibrosis.
- to investigate biomarkers of metabolism, inflammation, and fibrosis following multiple doses of GB1211 in healthy subjects and/or subjects with suspected NASH and liver fibrosis.
- to identify metabolites of GB1211 in plasma and urine.

2.2. Endpoints

2.2.1. Primary Endpoints

The primary safety endpoints for the study are as follows:

- incidence and severity of adverse events (AEs)
- incidence of laboratory abnormalities, based on haematology, clinical chemistry, and urinalysis test results
- 12-lead ECG parameters
- vital signs measurements
- physical examinations

2.2.2. Secondary Endpoints

For Part A, the single ascending dose (SAD) in healthy subjects, PK outcome endpoints of GB1211 are as follows:

- AUC from time zero to infinity ($AUC_{0-\infty}$)
- $AUC_{0-t_{last}}$
- C_{max}
- time of the maximum observed plasma concentration (T_{max})
- $t_{1/2}$
- apparent total plasma clearance (CL/F)
- apparent volume of distribution (V_z/F)
- amount of drug excreted in urine (A_e)
- percentage of dose excreted unchanged (f_e) in urine
- renal clearance (CL_R)

For Parts B and C, the multiple ascending doses (MAD) in healthy subjects and subjects with suspected NASH and liver fibrosis, PK outcome endpoints of GB1211 are as follows:

- AUC over a dosing interval ($AUC_{0-\tau}$)
- $AUC_{0-\infty}$
- C_{max}
- T_{max}
- $t_{1/2}$
- minimum observed plasma concentration (C_{min})
- observed accumulation ratio based on $AUC_{0-\tau}$ ($RA_{AUC_{0-\tau}}$)
- observed accumulation ratio based on C_{max} ($RA_{C_{max}}$)

Other PK parameters may also be reported if necessary.

2.2.3. Exploratory Endpoints

- The following biomarkers related to the GB1211 activity and biomarkers of metabolism, inflammation, and fibrosis will be assessed as follows:
 - For all SAD and MAD cohorts (Parts A, B, and C):
 - Serum galectin-3
 - Chemokine (C-C motif) ligand (CCL)-4
 - Other biomarkers may also be measured in an exploratory fashion.

- For MAD cohorts only (Parts B and C):
 - Changes from baseline at Day 10 (healthy subjects) and Day 42 (subjects with suspected NASH and liver fibrosis) in fasting plasma glucose and insulin.
 - Changes from baseline at Day 10 (healthy subjects) and Day 42 (subjects with suspected NASH and liver fibrosis) in lipid profile.
 - Changes from baseline at Day 10 (healthy subjects) and Day 42 (subjects with suspected NASH and liver fibrosis) in heat shock C-reactive protein (hsCRP), interleukin (IL)-12, monocyte chemotactic protein (MCP)-1, and tumor necrosis factor (TNF)- α , as well as the proinflammatory chemokines, CCL2, CCL3, CCL4, and the chemokine receptors chemokine (C-C motif) receptor (CCR)-1 and CCR2; and other biomarkers of inflammation as required.
- For subjects with suspected NASH and liver fibrosis only (Part C, MAD cohort):
 - Changes from baseline at Day 42 in biomarkers of fibrosis, including but not limited to extracellular matrix proteins (tissue inhibitor of matrix metalloproteinase-1 [TIMP-1], hyaluronic acid [HA], and aminoterminal peptide of pro-collagen III [P3NP]), A9, E74-like transcription factor (ELF) panel, cytokeratin (CK)-18, plasminogen activator inhibitor (PAI)-1, chitinase-3 like protein-1 (CH3L1), IL6, and pro-collagen 3.
- Identification of GB1211 metabolites in plasma and urine.

3. INVESTIGATIONAL PLAN

This is a Phase 1, randomised, double-blind, placebo-controlled, first-in-human study in which the safety, tolerability, and PK of orally administered GB1211 will be assessed in healthy adult subjects and adult subjects with suspected NASH and liver fibrosis.

Suspected NASH is defined as the presence or history of fatty liver, together with elevated alanine aminotransferase (ALT; defined as ALT values ≥ 30 U/L in males or ≥ 20 U/L in females), plus either confirmed type 2 diabetes mellitus (T2DM) or metabolic syndrome (Adult Treatment Panel III definition), in the absence of any other liver disease. Additional criteria aim to enrich for individuals with liver fibrosis (as per inclusion criteria; [Section 4.3](#)).

The study will consist of 3 parts: a SAD phase (Part A) enrolling a total of 5 cohorts of healthy subjects; a MAD phase (Part B) enrolling 2 cohorts of healthy subjects; and an optional Part C MAD phase, enrolling 1 cohort of subjects with suspected NASH and liver fibrosis. One cohort of Part A will receive GB1211 under both fasted and fed conditions to investigate the effect of food.

3.1. Overall Study Design and Plan

3.1.1. Part A

Part A will comprise a single-dose, sequential-cohort study incorporating a single-cohort, randomised, 2-part arm to investigate the effect of food. Overall, 40 subjects will be studied in 5 cohorts (Cohort A1 to A5), with each cohort consisting of 8 subjects.

Potential subjects will be screened to assess their eligibility to enter the study within 28 days prior to the first dose administration. Each subject will participate in 1 treatment period only, residing at the Clinical Research Unit (CRU) from Day -1 (the day before dosing) to Day 3 (48 hours postdose), except for the food-effect cohort (planned to be Cohort A3), where each subject will participate in 2 treatment periods separated by a minimum of 7 days.

All subjects will return for a Follow-up visit 5 to 7 days after their final dose.

Dose Regimen:

[figure not shown]
In each of Cohorts A1 to A5, 6 subjects will receive GB1211 and 2 will receive placebo. In all cohorts, except the food-effect cohort, all doses will be administered in the fasted state in accordance with a randomisation schedule on the morning of Day 1. For the food-effect cohort, which is planned to be Cohort A3, Treatment Period 1, Day 1 doses will be administered in the fasted state in accordance with the randomisation schedule and in Treatment Period 2, Day 1 doses will be given 30 minutes after the start of a high fat breakfast. Each subject in Cohorts A1 to A5 (except the food-effect cohort) will receive only a single dose of GB1211 or placebo during the study. In the food-effect cohort, subjects will receive the same treatment in both periods and will receive 2 single doses of GB1211 or placebo during the study.

In Cohorts A1 to A5 (except the fed period of the food-effect cohort), dosing will occur such that 2 subjects (1 active and 1 placebo) will be dosed at least 24 hours before the remaining subjects, where continuation to dose the remaining subjects will be at the Investigator's discretion.

Based on the ongoing review of the safety, tolerability, and PK results, additional nonresidential visits may be required. The number of additional visits per subject will not exceed 3 and will not extend beyond 28 days after each final dosing occasion.

[figure not shown]
An overview of the study design is shown in [Figure 1](#) and [Figure 2](#) and the planned dose levels in [Figure 3](#).

Figure 1: Study Schematic - Part A Cohorts (Except the Food-Effect Cohort)

[figure not shown]
Abbreviation: CRU = Clinical Research Unit

Figure 2: Study Schematic - Part A Food-Effect Cohort (Planned to be Cohort A3)

Abbreviation: CRU = Clinical Research Unit

Figure 3: Planned Dose Levels (Part A)

The total duration of study participation for each subject (from Screening through Follow-up visit) for all Part A cohorts except the food-effect cohort is anticipated to be approximately 5 weeks. For each subject in the food-effect cohort (planned to be Cohort A3), the total duration is anticipated to be approximately 6 to 7 weeks.

3.1.2. Part B

Part B will comprise a multiple-dose, sequential-cohort study. Overall, 22 subjects will be studied in 2 cohorts (Cohorts B1 to B2), with each cohort consisting of 11 subjects. Dosing in

Part B will start following review of safety, tolerability, and PK data from a single dose with exposure higher than the predicted steady-state exposure.

Potential subjects will be screened to assess their eligibility to enter the study within 28 days prior to the first dose administration. Each subject will participate in 1 treatment period only and reside at the CRU from Day -1 (the day before dosing) until the morning of Day 11 (24 hours after the final dose on Day 10).

[figure not shown]
All subjects will return for a Follow-up visit 5 to 7 days after their final dose.

Dose Regimen:

In each of Cohorts B1 to B2, 8 subjects will receive GB1211 and 3 subjects will receive placebo. The dietary state for dosing in Part B will be fasted unless data from the food-effect cohort is available and supports dosing in the fed state. For all subjects, the planned dosing will be BID on Days 1 to 9, inclusive, and a final single dose administration will occur in the morning of Day 10. The dosing interval/frequency and dosing duration in Part B may be changed following review of data from cohorts in Part A (Section 3.4). The predicted total daily exposure will not exceed the highest exposure observed in Part A. There will be a minimum of 10 days between dose escalations for each cohort.

[figure not shown]
An overview of the study design is shown in Figure 4 and the planned dose levels in Figure 5.

Figure 4: Study Schematic (Part B)

Abbreviations: BID = twice-daily; CRU = Clinical Research Unit

Figure 5: Planned Dose Levels (Part B)

Abbreviations: BID = twice-daily; TBD = to be determined

The total duration of study participation for each subject (from Screening through Follow-up visit) is anticipated to be approximately 6 to 7 weeks.

3.1.3. Part C (Optional)

Part C will comprise a multiple-dose cohort of 25 subjects with suspected NASH and liver fibrosis (Cohort C1). Part C may start following review of data from Part A and at least 1 Part B cohort.

Potential subjects will be screened to assess their eligibility to enter the study within 28 days prior to the first dose administration. Each subject will participate in 1 treatment period only and reside at the CRU from Day -1 (the day before dosing) until the morning of Day 2, returning for nonresidential visits on Days 7, 14, 21, 28, and 35. Subjects will then check back into the CRU on Day 41 until the morning of Day 43 (24 hours after the final dose on Day 42).

[figure not shown]
All subjects will return for a Follow-up visit 5 to 7 days after their final dose.

Dose Regimen:

For Part C, Cohort C1, 15 subjects will receive GB1211 and 10 subjects will receive placebo. The dietary state for dosing in Part C will be fasted unless data from the food-effect cohort is available and supports dosing in the fed state. For all subjects, the planned dosing will be BID on Days 1 to 41 inclusive, and a final single dose administration will occur in the morning of Day 42. The total daily dose administered, dose interval/frequency, and dosing duration will be based on review of data from Parts A and B.

An overview of the study design is shown in [Figure 6](#).

Figure 6: Study Schematic (Part C)

Abbreviations: BID = twice-daily; CRU = Clinical Research Unit

The dose level of Part C is to be determined following completion of Part A and at least 1 cohort of Part B.

The total duration of study participation for each subject (from Screening through Follow-up visit) for Cohort C1 is anticipated to be approximately 11 weeks.

A Schedule of Assessments is presented in [Appendix 6](#).

3.2. Study Start and End of Study Definitions

The start of the study is defined as the date the first subject, who is subsequently enrolled, signs an Informed Consent Form (ICF). The point of enrolment occurs at the time of subject number allocation. The end of the study is defined as the date of the last subject's last assessment (scheduled or unscheduled).

3.3. Additional Groups

Following review of the safety, tolerability, and PK data, additional dose cohorts (where systemic exposure is not expected to exceed that stated in the dose escalation stopping criteria [[Section 3.7](#)]) may be added to the study. Up to 3 further cohorts may be included in each of Parts A, B, and C. The requirement for additional cohorts will be agreed with the Sponsor and documented in the Trial Master File (TMF).

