3.6. Dose Escalation

Doses will be administered in an escalating manner following satisfactory review by the Sponsor and Investigator of the safety and tolerability data (up to 48 hours post-final dose) and PK data (up to 24 hours post-final dose) from the lower dose levels. Doses may be reduced and may be lower than the starting dose. There will be a minimum of 10 days between dose escalations to allow sufficient time for an adequate safety review.

Dose escalation in both Parts A and B will only occur if data from a minimum of 6 and 7 subjects, respectively, have been reviewed from the previous lower dose cohort, such that data from a minimum of 4 subjects who have received GB1211 will be used to make the dose escalation decision.

The justification for this is as follows:

- Based upon nonclinical data, no clinically important off-target effects are expected within the proposed dose range.
- A minimum of 4 subjects receiving the active drug is considered sufficient to characterise the safety profile and PK response to GB1211.

Between each dose escalation, the Investigator will review all available blinded data to ensure it is safe to proceed with the planned dose escalation. An interim safety report, summarising results from all available safety assessments, will be sent to the Sponsor prior to the start of each successive cohort. Any clinically significant results will be discussed with the Sponsor before dose escalation continues. Interim PK data will also be reviewed in terms of dose escalation and to confirm that the study design remains appropriate. In the event of a disagreement between Sponsor and Investigator on the dose escalation decision, the decision of the Investigator will be upheld.

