3.7. Dose Escalation Stopping Criteria

The study will be halted if 1 or more subjects experience an serious adverse event (SAE) that is considered to be related to IMP or 2 or more subjects experience severe AEs that are considered to be related to IMP. If, following an internal safety review, the Sponsor deems it appropriate to restart the study; this can be done following approval of a substantial protocol amendment.

In Parts A and B, following consultation with the Sponsor, dose escalation will stop if:

- One or more subjects in a cohort experience an SAE that is considered to be related to IMP or 2 or more subjects in a cohort experience severe AEs that are considered to be related to IMP.
- Clinically relevant signs or symptoms of similar nature occur in 2 or more subjects in a cohort that, in the opinion of the Investigator, warrant stopping of dose escalation.
- There is evidence of clinically significant increases in liver function tests (aspartate aminotransferase [AST], ALT, alkaline phosphatase, bilirubin, and/or gamma-glutamyl transferase), defined as 3 times the upper limit of normal (ULN) in 2 or more subjects in a cohort (confirmed with repeat testing), which are considered related to the IMP in the opinion of the Investigator.
- QT interval corrected for heart rate using Fridericia's method (QTcF) increases > 60 msec compared to baseline (predose) and/or absolute QTcF values > 500 msec (confirmed by repeat measurement) in 2 or more subjects in a cohort.
- The systemic exposure for any individual subject is predicted to exceed a C_{max} of 19755 ng/mL and/or an AUC from time zero to 24 hours postdose (AUC_{0-24}) of 52486 ng.h/mL; ie, systemic exposure will be no greater than the lowest exposure at the NOAEL (Criterion is based on preclinical toxicology data from both male and female mice, where no gender differences were observed in terms of safety findings).

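### Section 3.3 lets Part C add up to three dose cohorts, but the minimum-data rule (3.6) and the cohort-level liver, QTcF and similar-signs criteria (3.7) cover only Parts A and B

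*Protocol*

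**What the plan says.** Protocol section 3 describes "an optional Part C MAD phase, enrolling 1 cohort of subjects with suspected NASH and liver fibrosis". Section 3.1.3 sets that cohort, C1, at 25 subjects (15 GB1211, 10 placebo) with 42 days of dosing. Section 5.2 has most of those doses taken at home.

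Section 3.3 goes further: "Up to 3 further cohorts may be included in each of Parts A, B, and C". Its conditions are a review of safety, tolerability and PK data, agreement with the Sponsor, a record in the Trial Master File, and an exposure expectation, since it refers to "additional dose cohorts (where systemic exposure is not expected to exceed that stated in the dose escalation stopping criteria".

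Two sets of rules govern the step from one dose cohort to the next, and both name their scope:

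- Section 3.6: "Dose escalation in both Parts A and B will only occur if data from a minimum of 6 and 7 subjects, respectively, have been reviewed". The stated purpose is that "data from a minimum of 4 subjects who have received GB1211 will be used to make the dose escalation decision".
- Section 3.7: "In Parts A and B, following consultation with the Sponsor, dose escalation will stop if". The list that follows includes similar clinically relevant signs or symptoms in two or more subjects; related liver test increases, "defined as 3 times the upper limit of normal (ULN) in 2 or more subjects in a cohort (confirmed with repeat testing"; and a confirmed QTcF rise above 60 msec and/or a value above 500 msec in two or more subjects.

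No section gives Part C an equivalent. The SAP does not fill the gap: its section 6.3 confines it to Parts A and B.

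**The concern.** With a single patient cohort there is no next dose level, so limiting 3.6 and 3.7 to Parts A and B makes sense. Section 3.3 removes that premise by opening Part C to further dose cohorts, and the scope of the two rule sets was not extended to match.

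At stake is a decision between patient cohorts with no pre-set count or threshold, in the part with the longest dosing (42 days against a planned 10 in Part B), underlying liver disease and mostly unsupervised dosing. The missing criteria also match signals that the protocol itself reports: raised ALT in one mouse study (1.2), hERG inhibition (1.3), and QT/QTc increases in dogs that were judged non-adverse (1.4). Telemetry is not planned in Part C (7.3.4.2).

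**Working it through.** **1. The plan's own figure.** Under blinding, the number of GB1211 subjects guaranteed among those reviewed is the number reviewed minus all placebo subjects in the cohort. Part A (6:2): 6 − 2 = 4. Part B (8:3): 7 − 3 = 4. The stated minimum of 4 reproduces in both parts. Part C has no corresponding figure.

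**2. What does reach Part C.**

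- 3.7, opening paragraph: the study halts for one or more related SAEs, or for related severe AEs in two or more subjects. It is not limited by part.
- 3.3: brings in the 3.7 exposure limit for added cohorts.
- 3.5: total daily dose no higher than the maximum well-tolerated Part A dose, and limits on the fold increase between dose levels.
- 3.6, general text: satisfactory review by Sponsor and Investigator, an interim safety report before each successive cohort, and at least 10 days between escalations.
- 4.8: permanent stop for an individual on QTcF, exposure or liver chemistry.
- 4.9: discretionary termination.

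**3. A worked case.** Suppose 2 of the 15 GB1211 subjects in C1 have confirmed, related ALT between 3 and 5 times ULN, with normal bilirubin and INR, no symptoms or eosinophilia, and events neither severe nor serious.

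- In Part A or B, the 3.7 liver criterion is met and escalation stops, following consultation with the Sponsor.
- In Part C, the 3.7 list does not apply and the study-wide halt is not triggered. Neither subject meets a 4.8 liver criterion, because these need more than 5 times ULN, or more than 3 times ULN with a bilirubin, INR or clinical finding. The 3.6 review would see both cases, but the text attaches no cohort-level consequence to them.

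For QTcF the gap is narrower. Section 4.8 uses the same thresholds as 3.7, so each affected subject stops dosing. Only the consequence for the next cohort is missing.

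**4. Whether the Part A/B values would carry over.** Not directly.

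- *Minimum count.* In a 15:10 cohort, reviewing m blinded subjects guarantees max(0, m − 10) on GB1211. For m = 6 or 7 this is 0. If the m subjects are a random draw from the 25, the hypergeometric probability of at least 4 on GB1211 is 0.54 for m = 6 and 0.74 for m = 7. A guarantee of 4 would need 10 + 4 = 14 reviewed. That is arithmetic, not a proposed rule.
- *Two-subject trigger.* With n active subjects and per-subject probability p, P(2 or more) = 1 − (1 − p)^n − np(1 − p)^(n − 1). The values of p are assumed.

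| p | n = 6 (Part A) | n = 8 (Part B) | n = 15 (C1) |
|---|---|---|---|
| 0.02 | 0.006 | 0.010 | 0.035 |
| 0.05 | 0.033 | 0.057 | 0.171 |
| 0.10 | 0.114 | 0.187 | 0.451 |

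- *Liver threshold.* Section 4.6 excludes ALT above 155 U/L (females) and 185 U/L (males). The ULN is not given. If it is at or below 155/3 = 51.7 U/L or 185/3 = 61.7 U/L respectively, a patient could enter already at 3 times ULN. With a higher ULN the overlap disappears.

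**5. Size.** Section 3.3 gives no size for added cohorts. At the C1 size and allocation (an assumption): 3 × 25 = 75 further subjects, of whom 3 × 15 = 45 on GB1211.

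**The case against.** The strongest reply is that a higher-dose C2 could not open unexamined. Section 3.6 requires a satisfactory review and an interim safety report, and upholds the Investigator's decision in a disagreement. The dose is capped at a level tolerated in Part A. Part C is optional with one planned cohort, 3.4 assigns the ascending design to Parts A and B, and 3.3 does not say that added cohorts must go up in dose. The omission may be deliberate, since healthy-volunteer thresholds may not suit patients who enter with raised ALT. Even in Parts A and B the liver criterion depends on the Investigator's causality opinion.

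Most of this stands, and it rules out several stronger readings that a reader might infer:

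- *Part C has no stopping rules.* The study-wide halt and the individual stops apply to it.
- *QTcF or liver findings in patients have no consequence.* Section 4.8 acts on the individual; what is absent is the cohort-level consequence.
- *Escalation in patients is planned.* It is only possible: Part C is called a MAD phase and its dose is still to be determined. SAP section 7 lists Part A treatments that are not in protocol Table 3 (400 mg, and 50 mg as ten 5 mg capsules). This suggests that the freedom to vary dose groups was used there, but it shows nothing about Part C.
- *Cohorts can be added without an amendment.* Section 3.3 asks for Sponsor agreement and a file record but does not say that an amendment is unnecessary. Appendix 5 requires ethics approval, and regulatory approval as locally required, for substantial amendments.

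What the reply does not supply is a numeric trigger or a minimum count for Part C. If the omission is deliberate, the protocol does not say so or name what replaces the criteria.

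**Conclusion.** The concern holds as a mismatch of scope between 3.3 and the two rule sets in 3.6 and 3.7. If a further Part C cohort were opened at a higher dose, the decision would rest on general review. No stated minimum of reviewed C1 subjects would apply, and no cohort-level liver, QTcF or similar-signs criterion. The clearest instance is the pair of ALT rises between 3 and 5 times ULN in the worked case.

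The point should be corrected before any Part C extension. It does not undermine Parts A and B, or C1 taken alone. The figure of up to 75 subjects (45 on GB1211) assumes that all three added cohorts are used at the C1 size and allocation. The possible overlap of entry ALT with 3 times ULN depends on a ULN that the documents do not give.

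**What to change.** Reconcile 3.3, 3.6 and 3.7 in one of two ways:

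- remove Part C from the additional-cohort sentence in 3.3, so that C1 is the only patient dose level; or
- keep it, and state in 3.6 the minimum number of reviewed subjects between Part C cohorts, and in 3.7 which cohort criteria apply there.

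Under the second option, the minimum should be worked out for the allocation actually used rather than copied from Parts A and B, and any liver criterion should be checked against the Part C entry limits. The thresholds themselves are for the sponsor and investigator to decide.

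The cost is protocol wording. Appendix 6 already schedules the clinical laboratory tests and ECGs in Part C. The downside is less freedom to add Part C dose levels.
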